### **3.1.4 Long-Term Follow-up**

Patients should continue onto Long-Term Follow-up after completing the End-of-Treatment Follow-up Period.

Patients will be followed every 12 weeks for survival, or more frequently as needed. Patients who discontinue treatment while showing clinical benefit (complete response [CR], partial response [PR], or stable disease [SD]) should have tumor assessments during these visits for duration of response.

Long-term Follow-up for survival may be conducted by telephone, rather than by an in-person visit, once tumor progression is determined or use of subsequent anti-cancer therapy has been initiated. During the Long-Term Follow-up Period, if the patient undergoes local therapy (e.g., resection, radiation) or new systemic therapy is initiated, this should be documented.

### **3.1.5 Study Duration**

Patients who receive study drug(s) may continue as long as they experience clinical benefit in the opinion of the Investigator or until unacceptable toxicity or symptomatic deterioration attributed to disease progression as determined by the Investigator after an integrated assessment of radiographic data, biopsy results (if available), and clinical status, or withdrawal of consent.

### **3.1.6 Stopping Rules**

#### **3.1.6.1 Stopping Rules for All Cohorts**

Management of drug-related toxicities will follow the adverse event management tables ([Appendix F](#) and [Appendix G](#)). Management of drug-related laboratory abnormalities will follow the management tables in Appendix H.

The Sponsor will discuss such cases with the study Investigators as appropriate to determine further enrollment. IRBs may be notified by the Investigators of all cases and decisions regarding continued enrollment, according to applicable regulatory requirements or institution procedures.

#### **3.1.6.2 Stopping Rules for Clinical Deterioration**

Accumulating clinical evidence indicates that the emergence of objective responses to agents that activate anti-tumor immune responses may follow delayed kinetics of weeks or months, and can be preceded by initial apparent progression of disease with the appearance of new lesions or some enlarging of lesions while certain index lesions are regressing (“mixed response”). Therefore, it is reasonable to allow patients who experience apparent progression to continue to receive treatment until progression is confirmed at the next imaging assessment. These

considerations should be balanced by clinical judgment as to whether the patient is clinically deteriorating and unlikely to receive any benefit from continued treatment.

Such deterioration will be assessed to have occurred after a clinical event that, in the Investigator's opinion, is attributable to disease progression and is unlikely to reverse with continued study treatment and therefore indicates that the patient is not benefiting from study treatment and cannot be managed by the addition of supportive care. The decision to continue treatment should be discussed with the Sponsor's Medical Monitor or designee. Examples of events that may, in the Investigator's opinion, indicate a lack of clinical benefit include but are not limited to the following:

- Eastern Cooperative Oncology Group (ECOG) score increase of at least 2 points from baseline (e.g. from 0 to 2).
- Habitual changes such as changes in activities and symptoms including reduction in appetite and/or sleep, altered awareness, and increased pain-related symptoms due to cancer.
- Progression of disease confirmed by the treating Investigator.
- Any setting where the initiation of new anti-neoplastic therapy has been deemed beneficial to the patient even in the absence of any such documented clinical events.

### **3.2 Study Population**

#### **3.2.1 Planned Number of Patients and Study Centers**

The total number of patients planned for this study is estimated to be 295 in North America. By the end of the study, approximately 85 patients in Part 1a (approximately 20 in monotherapy dose escalation, 15 in combination dose escalation, 10 in an 3-week dose regimen, and up to 40 in exploration cohorts) and 210 patients in Part 1b (approximately 30 patients for each of the 7 Phase 1b cohorts) will be enrolled. There will be approximately 50 study centers participating in this study.

#### **3.2.2 Inclusion Criteria for All Cohorts**

For entry into the study, *all* of the following criteria must be met.

1. Patients must have at least one measurable lesion at baseline by computed tomography (CT) or magnetic resonance imaging (MRI) as per RECIST v1.1 criteria.
  - a. Tumor sites situated in a previously irradiated area, or in an area subjected to other loco-regional therapy, are not considered measurable unless there has been demonstrated progression in the lesion.
  - b. Sites for biopsy must be *distinct from target lesions used for efficacy assessment*.
2. Patients must have had progressive disease on, or refused, appropriate approved therapy for their tumor type unless otherwise specified in the cohort specific criteria; for example, all

NSCLC patients should have progressed on platinum doublet chemotherapy, and appropriate approved therapy for patients with EGFR or ALK mutations.

3. All patients in Phase 1a and patients who consent to be biopsied in Phase 1b must have at least 1 tumor site that can be biopsied and be willing to have pre-treatment and on-treatment tumor and skin biopsies (optional for patients in the GBM cohort). Biopsies will be performed according to the treating institution's own guidelines from a minimum of 10 patients in each Phase 1b cohort. If biopsy has been performed and adequate sample collected as part of the patient's standard of care within 28 days prior Cycle 1 Day 1, it does not need to be repeated if the sample is available.
4. Understand and sign an IRB/IEC-approved ICF prior to any study-specific evaluation
5. Age  $\geq 18$  years
6. ECOG performance status of 0 or 1
7. Willing and able to comply with all study procedures
8. Prior focal radiotherapy must be completed at least 2 weeks before first dose of study drug administration. No radiopharmaceuticals (strontium, samarium) within 8 weeks before first dose of study drug administration.
9. Prior surgery that requires general anesthesia must be completed at least 1 week before first dose of study drug administration. Surgery requiring local/epidural anesthesia must be completed at least 72 hours before first dose of study drug administration and patients should have recovered.
10. Screening laboratory values must meet the following criteria:

#### **Hematologic**

- a. Neutrophils  $\geq 1500$  cells/  $\mu\text{L}$
- b. Platelets  $\geq 100 \times 10^3/ \mu\text{L}$
- c. Hemoglobin  $\geq 9.0$  g/dL

Serum creatinine  $\leq 1.5 \times$  ULN or creatinine clearance of  $\geq 40$  mL/minute (using Cockcroft/Gault Formula)

$$\text{Female CrCl} = \frac{(140 - \text{age in years}) \times (\text{weight in kg}) \times 0.85}{72 \times (\text{serum creatinine in mg/dL})}$$

$$\text{Male CrCl} = \frac{(140 - \text{age in years}) \times (\text{weight in kg})}{72 \times (\text{serum creatinine in mg/dL})}$$

- d. PT/INR  $\leq 1.5 \times$  ULN and PTT (aPTT)  $\leq 1.5 \times$  ULN

**Hepatic**

- a. AST or ALT  $\leq 3$  x ULN
  - b. Bilirubin  $\leq 1.5$  x ULN (except patients with Gilbert's syndrome, who must have total bilirubin  $< 3$  mg/dL)
  - c. Albumin  $> 3.0$  g/dL (pancreatic cancer patients only)
11. Women of childbearing potential (WOCBP) must have a negative serum  $\beta$ -human chorionic gonadotropin ( $\beta$ -hCG) at screening and agree to use a reliable form of contraception (e.g., oral contraceptives, intrauterine device, or double barrier method of condom and spermicide) for at least 28 days prior to the dosing of any study drug and for at least 23 weeks after the last dose of any study drug.
  12. Men who are sexually active with WOCBP must agree to follow instructions for method(s) of contraception for the duration of treatment with study drugs plus 31 weeks post-treatment completion.

**3.2.3 Exclusion Criteria for All Cohorts**

Patients who meet ANY of the following criteria will be excluded from study entry.

1. Current or history of clinically significant muscle disorders (e.g., myositis), recent unresolved muscle injury, or any condition known to elevate serum CK levels
2. Immunosuppressive doses of systemic medications, such as steroids or absorbed topical steroids (doses  $> 10$  mg/day prednisone or equivalent daily) must be discontinued at least 2 weeks before study drug administration except in the case of tumor-related AE treatment. Patients with a condition requiring chronic systemic treatment with either corticosteroids (inhaled or topical steroids and adrenal replacement steroid doses  $> 10$  mg/day prednisone equivalent) or other immunosuppressive medications within 2 weeks of treatment are permitted in the absence of active autoimmune disease (except for patients with glioma).
3. Decreased cardiac function with NYHA  $> Class 2$
4. Uncontrolled or significant heart disorder such as unstable angina
5. Significant abnormalities on ECG at screening. QTcF  $> 450$  msec for males or  $> 470$  msec for females at screening
6. History of anti-drug antibodies, severe allergic, anaphylactic, or other infusion-related reaction to a previous biologic agent
7. Known history of sensitivity to infusions containing Tween 20 (polysorbate 20) and Tween 80 (polysorbate 80)
8. Consumption of non-pasteurized milk while on study drug and for 30 days after discontinuing study drug

9. Non-oncology vaccine therapies for prevention of infectious diseases (e.g., HPV vaccine) within 4 weeks of study drug administration. The inactivated seasonal influenza vaccine can be given to patients before treatment and while on therapy without restriction. Influenza vaccines containing live virus or other clinically indicated vaccinations for infectious diseases (i.e., pneumovax, varicella, etc.) may be permitted, but must be discussed with the Sponsor's Medical Monitor and may require a study drug washout period prior to and after administration of vaccine.
10. Current unresolved infection or history of chronic, active, clinically significant infection (viral, bacterial, fungal, or other) which, in the opinion of the Investigator, would preclude the patient from exposure to a biologic agent or pose a risk to patient safety
11. Positive test for latent tuberculosis (TB) at screening (e.g. T-SPOT or Quantiferon test) or evidence of active TB
12. Patients with abnormal serum chemistry values, which in the opinion of the Investigator is considered to be clinically significant, will be excluded from the study. This will include patients who show clinical signs and symptoms related to their abnormal serum chemistry values as well as patients whose serum chemistry values are asymptomatic but clinically significant (e.g. hypokalemia or hyponatremia).
13. Lack of peripheral venous or central venous access or any condition that would interfere with drug administration or collection of study samples
14. Any uncontrolled medical condition or psychiatric disorder which, in the opinion of the Investigator, would pose a risk to patient safety or interfere with study participation or interpretation of individual patient results
15. Concomitant use of statins while on study. However, a patient using statins for over 3 months prior to study drug administration and in stable status without CK rise may be permitted to enroll
16. Pregnant or breastfeeding
17. Active, known, or suspected autoimmune disease. Patients with type I diabetes mellitus, hypothyroidism requiring only hormone replacement, skin disorders (such as vitiligo, psoriasis, or alopecia) not requiring systemic treatment, or conditions not expected to recur in the absence of an external trigger are permitted to enroll.
18. Treatment with any anti-cancer therapy or participation in another investigational drug or biologics trial within 28 days or  $\leq 5$  half-lives (whichever is shorter) prior to first dose of study drug administration or while on this study
19. Known history of testing positive for human immunodeficiency virus (HIV) 1 or 2 or known acquired immunodeficiency syndrome (AIDS)

20. Positive test for hepatitis B virus surface antigen (HBsAg) or detectable hepatitis C virus ribonucleic acid (HCV RNA) indicating acute or chronic infection
21. Symptomatic interstitial lung disease or inflammatory pneumonitis
22. Untreated or active central nervous system (CNS) or leptomeningeal metastases. Patients are eligible if metastases have been treated and patients are neurologically returned to baseline or neurologically stable (except for residual signs or symptoms related to the CNS treatment) for at least 2 weeks prior to first dose of study drug administration. In addition, patients must be either off corticosteroids, or on a stable dose or decreasing dose of  $\leq 10$  mg daily prednisone or prednisone equivalent (except for patients with glioma).
23. Evidence of coagulopathy or bleeding diathesis
24. Any uncontrolled inflammatory GI disease including Crohn's Disease and ulcerative colitis
25. Prior exposure to any CSF1R pathway inhibitors
26. Transfusion completed within 72 hours prior to first dose of study drug administration

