**3.4 Discontinuation of Patients following any Treatment with Study Drug**

Patients **must** discontinue study drugs for any of the following reasons:

- Withdrawal of informed consent (patient’s decision to withdraw for any reason)
- Any clinically significant AE, abnormal laboratory test results, or intercurrent illness which, in the opinion of the Investigator, indicates that continued participation in the study is not in the best interest of the patient
- Patients who are required to have prohibited concomitant medications

- Pregnancy
- Termination of the study by the Sponsor
- Loss of ability to freely provide consent through imprisonment or involuntary incarceration for treatment of a psychiatric or physical (e.g., infectious disease) illness
- Documented disease progression or clinical deterioration while receiving active study therapy
- Non-compliance by the patient

All patients who discontinue study treatment should comply with protocol specified follow-up procedures as outlined in Section 5.2.4. The only exception to this requirement is when a patient withdraws consent for all study procedures or loses the ability to consent freely (i.e., is imprisoned or involuntarily incarcerated for the treatment of a psychiatric or physical illness).

If a patient was discontinued, the reason for discontinuation must be entered on the appropriate CRF. The date and reason for cessation of cabiralizumab and/or nivolumab will be documented, and the Investigator must make every effort to perform the End-of-Treatment Visits. Adverse event reporting will continue until 100 ( $\pm 7$ ) days after the last dose of study drug or until initiation of subsequent anti-cancer therapy. Patients with ongoing SAEs will be followed until resolution or stabilization.

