#### **4.4 Method of Assigning Patient Identification**

Patients must be able to provide written informed consent and meet all eligibility criteria. No waivers of inclusion or exclusion criteria will be granted by Sponsor or its designee for any patient enrolled in the study. Before enrolling a patient, all eligibility criteria must be satisfied.

Patients who qualify for Phase 1a dose escalation of the study will be enrolled as follows:

- The 2 mg/kg cabiralizumab monotherapy cohort was enrolled first, followed by enrollment to the 1mg/kg cabiralizumab /nivolumab combination cohort. Patients in these cohorts will be treated for a total of two 14-day treatment cycles within the DLT period.
- Enrollment into the 4 mg/kg cabiralizumab monotherapy cohort will proceed once the DLT period is cleared in preceding monotherapy cohorts.
- Dose escalation into increasing dose levels of cabiralizumab in combination with nivolumab may proceed until DLTs are observed either in the cabiralizumab monotherapy or the cabiralizumab in combination with nivolumab cohorts after discussion and agreement by the Cohort Review Committee.

In 3-week dosing regimen Cohort (1aD), approximately 10 patients will be enrolled into the 4 mg/kg cabiralizumab in combination with nivolumab cohort. These patients will receive study treatment every three weeks.

The Phase 1a exploration consists of six cohorts of approximately 10 patients each. These cohorts are further evaluating the safety, PK, and PD of cabiralizumab as monotherapy and in combination with nivolumab.

In Phase 1b, approximately 30 patients will be enrolled per cohort. Enrollment will be open for all cohorts in parallel and will continue until the enrollment target is reached. Once a cohort is filled, further enrollment will be restricted to the cohort(s) that have not been filled. A total of approximately 210 patients will be enrolled in the Phase 1b arm of the study.

The Investigator may repeat qualifying lab tests and vitals/ECGs prior to enrollment if a non-qualifying finding is considered an error or an acute finding is likely to meet eligibility criteria upon repeat testing.

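### Exclusion 2 is mis-drafted: its second sentence largely cancels the 2-week washout for chronic users of other immunosuppressants, and its closing glioma clause is unclear

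*Protocol*

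**What the plan says.** Exclusion 2 appears with the same wording in the protocol synopsis and in section 3.2.3. It has two sentences.

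- **Sentence 1** covers immunosuppressive doses of systemic medications. Steroids and absorbed topical steroids are its examples, with a threshold of more than 10 mg/day prednisone equivalent. These "must be discontinued at least 2 weeks before study drug administration except in the case of tumor-related AE treatment".
- **Sentence 2** concerns patients whose condition needs "chronic systemic treatment with either corticosteroids (inhaled or topical steroids and adrenal replacement steroid doses" above 10 mg/day prednisone equivalent), and continues with "other immunosuppressive medications within 2 weeks of treatment are permitted in the absence of active autoimmune disease (except for patients with glioma").

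Four other provisions bear on how this is read:

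- Exclusion 17 in the same list bars "Active, known, or suspected autoimmune disease", with stated exceptions such as type I diabetes and skin disorders that need no systemic treatment.
- Exclusion 22 (CNS metastases) requires patients to be off corticosteroids or on a stable or falling dose of at most 10 "mg daily prednisone or prednisone equivalent (except for patients with glioma").
- Cohort 1b7 inclusion 4 (section 3.2.4.2.7) asks that glioma patients who take steroids be on a stable or decreasing dose for at least 5 days before the baseline MRI. It names no maximum dose.
- Section 4.4 states: "No waivers of inclusion or exclusion criteria will be granted by Sponsor or its designee for any patient enrolled in the study".

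**The concern.** Both drugs in the combination act on the immune system, and section 4.3.9 classes both as immuno-oncology agents. A washout of immunosuppressants before the first dose is a natural entry condition. Sentence 2 gives back much of what sentence 1 takes away: a patient on a short course of a systemic immunosuppressant has to stop, while a patient on the same kind of drug chronically may enter without stopping.

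Because no waivers are granted, sites should apply the criterion as it stands. At stake are the safety of patients who enter while immunosuppressed and the make-up of the Phase 1b cohorts in which the objective response rate (ORR) is estimated. For the glioma cohort, two sites could read the closing parenthesis in opposite directions and reach different decisions on the same patient.

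**Working it through.** No calculation applies to the wording. The check sets the provisions side by side.

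1. **Scope of the washout.** Sentence 1 gives steroids as examples, so it reaches other systemic immunosuppressants. Its only dose measure is in prednisone equivalents, and its only stated exception is tumor-related AE treatment.

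2. **Scope of the permission.** Sentence 2 applies to the same 2 weeks. Its bracketed qualifier (inhaled, topical, adrenal replacement) belongs to the corticosteroids. The other immunosuppressants get no dose, no drug names and no approval step inside the criterion.

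3. **What the one condition adds.** The permission depends on there being no active autoimmune disease. Exclusion 17 already removes active, known or suspected autoimmune disease, apart from its listed exceptions, so the condition adds little. It also does not reach immunosuppression given for a non-autoimmune reason. For chronic users the washout is therefore largely cancelled.

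4. **Signs of a drafting slip.** Sentence 2 lists inhaled and topical steroids under systemic treatment. The glioma parenthesis, which in exclusion 22 follows a restriction, here follows a permission.

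5. **Readings of the glioma parenthesis.** Take a 1b7 patient on systemic steroids.
   - At or below 10 mg/day prednisone equivalent, the stated threshold in sentence 1 is not exceeded. The patient passes under every reading.
   - Above 10 mg/day but covered by the exception for tumor-related AE treatment, the patient also passes.
   - Above 10 mg/day and outside that exception, the result depends on the reading. If the parenthesis withdraws the permission (the literal reading), the washout applies and the patient is excluded. If it lifts only the autoimmune condition, the result turns on whether the bracketed steroid list is exhaustive. If it exempts glioma from the whole criterion, in line with exclusion 22, the patient is admitted.

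6. **Size.** Section 3.2.1 plans about 210 Phase 1b patients in 7 cohorts: 210 / 7 = about 30 in cohort 1b7. The glioma question can touch 0 to about 30 planned patients. The upper end is the cohort size and not an estimate. The documents give no count of patients on chronic immunosuppressants or of glioma patients above 10 mg/day, so no affected share can be computed.

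**The case against.** **A rule followed by an exception is ordinary drafting.** Exclusions 9, 15 and 17 have the same shape, and the statin exception in exclusion 15 names no drug or dose either. This stands in part: sentence 2 can be read as an intended carve-out, so a strict contradiction is not shown. But the statin exception requires more than 3 months of prior use and stable status without a CK rise, and the vaccine exception requires discussion with the Medical Monitor. The permission in exclusion 2 has no comparable bound.

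**The limits may sit elsewhere.** Section 3.4 lists among the reasons for stopping study drug: "Patients who are required to have prohibited concomitant medications". The text between sections 3.2.5 and 3.4 is redacted. A reader might infer that the protocol nowhere restricts these drugs, and the documents do not support that. The point is confined to exclusion 2 and says nothing about the redacted text. If a prohibited list does cover these drugs, exclusion 2 admits patients who would then have to discontinue. If it does not, the permission is open-ended. The criterion needs rewording in either case.

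**Other criteria shrink the group.** This stands. Exclusion 10 (infection), 17 (autoimmune disease), 21 (symptomatic interstitial lung disease or pneumonitis) and 24 (uncontrolled inflammatory GI disease) remove many patients who would need chronic immunosuppression. Cohort 1b2 also bars prior mTOR inhibitors. The sponsor or its designee approves enrollment (section 7.2). Exclusion 14 covers uncontrolled conditions that, in the investigator's opinion, "would pose a risk to patient safety or interfere with study participation or interpretation of individual patient results". It does not reach a patient who is well controlled on a chronic immunosuppressant.

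**Inclusion 4 of cohort 1b7 does not conflict with exclusion 2.** Correct. A reader might infer a contradiction, but inclusion 4 only sets a stability condition on patients who take steroids. It grants no dose above 10 mg/day, and both rules can hold together. The ambiguity is confined to the narrow group in the last case of step 5.

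**Conclusion.** The point holds as a drafting fault in one eligibility criterion, and it is minor. As written, exclusion 2 imposes a 2-week washout and then largely lifts it for chronic users of other systemic immunosuppressants, on a condition that exclusion 17 largely duplicates. Its glioma clause can be read to admit or to exclude 1b7 patients above 10 mg/day prednisone equivalent who are outside the exception for tumor-related AE treatment.

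A reader might go further and infer that the ORR estimates or the safety results are materially distorted. The documents do not support that: the number affected cannot be derived, and no endpoint, analysis population, sample size or decision rule depends on this wording.

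The conclusion rests on two assumptions. Sites apply the criterion literally, as the no-waiver rule implies. The sponsor meant the washout to cover non-steroid immunosuppressants as well; this is inferred from sentence 1 and from the signs of a slip in sentence 2, and the protocol does not state it.

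**What to change.** After the sponsor confirms its intent, replace exclusion 2 in both the synopsis and section 3.2.3 with:

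> Patients with a condition requiring systemic corticosteroids or absorbed topical steroids (>10 mg/day prednisone equivalent) or immunosuppressive doses of other systemic medications within 2 weeks before first dose are excluded, except for tumor-related AE treatment and except glioma patients on steroids who meet cohort 1b7 inclusion 4. Inhaled steroids, topical steroids not exceeding that absorbed-dose limit, and adrenal replacement steroids (including >10 mg/day prednisone equivalent) are permitted in the absence of active autoimmune disease.

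This keeps the dose qualifier of sentence 1 and the existing steroid allowances, and it states the glioma exception directly. Inclusion 4 has no dose cap, so the sponsor should confirm that none is wanted for glioma. If the sponsor does mean to admit patients on chronic non-steroid immunosuppressants, it should instead name the drugs and maximum doses and say whether glioma patients are inside or outside the permission.

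The cost is an amendment to one criterion in two places. A small but unknown number of patients on chronic immunosuppressants would become ineligible.
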